**3.4. SUBJECT WITHDRAWAL****A. Voluntary Participation:**

It is recognized that the subject's participation in this trial is entirely voluntary, and that she/he may refuse to participate and may withdraw from participation at any time without jeopardy to any future medical care. It is also recognized that the investigator, at his/her discretion, may withdraw a subject from this study based upon his/her professional judgment. In event of subject withdrawal, applicable local procedures should be followed. Patients who are withdrawn from the study will not be replaced, and a Withdrawal form should be completed.

**B. Withdrawals:** All subject withdrawals must be documented on the Withdrawal Form. If withdrawal is due to patient death, or removal of components as indicated below, a withdrawal form should be completed. If the patient is withdrawn after receiving the randomized treatment, the subject will NOT be replaced.

**C.** If a patient receives a partial revision (patella or polyethylene replacement), or a reoperation (e.g.: manipulation), this should be documented on an adverse event form and the patient should continue to be followed in the study.

**D. Subject Withdrawal Criteria:**

1. If patients meet any of the following criteria, a subject withdrawal form should be completed, and below data documented on the form:
  - a. Patient rescinds consent in writing: Date of occurrence
  - b. Patient Death: Reason and date of death should be documented, and any relation to study device.
  - c. Removal: Date of revision, all component part numbers removed, reason for revision, and any relation to study device.
  - d. Revision of Metal\* Components (Femur or Tibia): date of revision, all component part numbers removed, and reason for revision

*\*Bearing revisions in which only the polyethylene is replaced will not be withdrawn from the study.*

## **Vanguard XP Randomized Controlled Clinical Outcomes Protocol**

---

### **4. REVISION / REMOVAL**

For subjects whom are revised in which a partial (revision) or full revision (removal) is conducted, an adverse event form should be completed. In patients in which metal or all components (removal) are removed, a withdrawal form should also be completed.

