**2.5. PRIMARY AND SECONDARY ENDPOINTS**

- A. Primary Endpoint: Percentage of patients reporting their knee feels “normal”.
- B. Secondary Endpoints: Patient Reported Outcome Measures “PROMs”, Knee Society Score, Complication Rate, Pain Relief, Functional outcomes, Survivorship

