## 2.6. ASSESSMENT PROCEDURE

**Table 2.6-A**

Form	Pre-op (screening)	Operative (Enrollment)	Discharge	3 Mos	6 Mos	1 Yr	2 Yrs	3 Yrs	5 Yrs	7 Yrs	10 Yrs
Screening Log	X										
Informed Consent	X										
Demographics / Medical History	X										
Operative Form		X									
Modified Knee Society Score*	X		X	E†	SC***	X	X				
PROMS** Questionnaire	X		X	E†	SC***	X	X	X	X	X	X
Radiographs: AP, ML, Skyline			X	E†	SC***	X	X				
Radiographic Form			X			X	X				
Adverse Events		AS NEEDED	AS NEEDED	AS NEEDED	AS NEEDED	AS NEEDED	AS NEEDED	AS NEEDED	AS NEEDED	AS NEEDED	AS NEEDED
Withdrawals		AS NEEDED	AS NEEDED	AS NEEDED	AS NEEDED	AS NEEDED	AS NEEDED	AS NEEDED	AS NEEDED	AS NEEDED	AS NEEDED
Protocol Deviations		AS NEEDED	AS NEEDED	AS NEEDED	AS NEEDED	AS NEEDED	AS NEEDED	AS NEEDED	AS NEEDED	AS NEEDED	AS NEEDED

\*Modified Knee Society Score includes an additional assessment of incidence of anterior knee pain. This additional question is exploratory and will not affect the total score of the KSS. In the event that a patient does not return for a visit, a partial “Phone Knee Society Score” can be completed and entered into the database.

\*\*Patient Administered Outcome Scores “PROMS” Questionnaire can be collected in the office, over the phone, or via mailer. The questionnaire contains SANE/Patient Satisfaction, Oxford Knee Score, EQ-5D, KOOS, and the Forgotten Joint Score validated patient administered outcomes scores. These scores are combined into the paper version for easier administration to patients for completing. When entering to Joint Assist, these scores will be separated but contain the same exact questions.

\*\*\*SC: 6 Month visit should be collected only if standard of care. Radiographs should be taken if standard of care at the center, however no radiographic form will be collected. Any adverse event or failure determined from radiographs should be documented on an adverse event form. All visits will be documented relative to the clinical site in the approved informed consent.

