**I. Withdrawal**

Occurrence of death, rescinded consent, randomization failure after surgery commenced, or when the subject has a complete removal, or revision of metal components (femoral component / tibial tray).

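### The primary 'feels normal' test has no stated rule for knees withdrawn after implant removal or metal revision; the implied handling drops them, with no sensitivity analysis

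*Combined protocol and SAP*

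**What the plan says.** **Which revisions end follow-up.** Section 4 asks for an adverse event form after any revision, and adds: "In patients in which metal or all components (removal) are removed, a withdrawal form should also be completed". Section 3.4 D lists removal, and revision of a metal femoral or tibial component, as withdrawal criteria. Section 15 I defines withdrawal to include cases "when the subject has a complete removal, or revision of metal components (femoral component / tibial tray". Withdrawn subjects are not replaced (3.4 A and B).

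**Which do not.** For a patella or polyethylene revision, or a reoperation, 3.4 C says "this should be documented on an adverse event form and the patient should continue to be followed in the study". Section 3.4 D confirms this for the bearing: "Bearing revisions in which only the polyethylene is replaced will not be withdrawn from the study".

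**The primary analysis.** The endpoint in 2.5 is "Percentage of patients reporting their knee feels" normal. Section 8.2 gives a two-sided Pearson chi-square test at p<0.05. It states no analysis set, denominator, primary time point or status for a withdrawn knee. Section 9, despite its title on missing data, covers data entry, reimbursement and phone follow-up. Section 8.1 needs 137 per group and enrols 153, to allow 10% for patients who do not follow up.

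**Where revisions are visible.** The secondary endpoints in 2.5 include "Complication Rate, Pain Relief, Functional outcomes, Survivorship", and the annual report in 11.1 lists revisions and withdrawals. No text links these to the primary test.

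**The concern.** The trial compares two implants, so losing the implant is itself a result of treatment and not an ordinary missed visit. Yet the plan ends follow-up for exactly those knees and keeps collecting data on milder failures. A knee withdrawn before the primary assessment has no answer at that assessment. It may have earlier PROMS answers, but nothing says whether they would count.

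Comparing all knees as randomized and comparing only knees that kept their metal components are different questions, and the plan does not say which one the primary p-value answers. If the choice is made after the data are seen, it can decide a borderline result.

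**Working it through.** **1. The plan's own figure.** Inputs from 8.1: proportions 0.66 and 0.83, two-sided alpha 0.05, power 90%. I take 0.66 as CR and 0.83 as XP, because the stated goal is that XP feels more normal. The mean proportion is 0.745.

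n per arm = [1.960·√(2·0.745·0.255) + 1.2816·√(0.66·0.34 + 0.83·0.17)]² / 0.17² = (1.2081 + 0.7748)² / 0.0289 = 136.05, rounded up to 137.

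137/0.90 = 152.2, rounded up to 153 per arm, 306 in total. Power at 137 per arm is 90.2%. The plan's arithmetic reproduces. It also shows that the 137 are knees remaining after loss, which is the nearest the documents come to implying that withdrawn knees are outside the denominator.

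**2. Two ways to count a withdrawn knee.** Let r be the share of knees with removal or metal revision before the primary assessment. The documents give no value, so every r below is an assumption. Suppose 66% and 83% hold among unrevised knees.
- Left out: the proportions stay 0.66 and 0.83, a gap of 17.0 points.
- Counted as not normal: the proportions become 0.66·(1−r_CR) and 0.83·(1−r_XP).

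Example at 1%/3%: 0.83·0.97 − 0.66·0.99 = 0.8051 − 0.6534 = 0.1517.

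For each case, 400,000 trials were simulated with 137 knees per arm: the number revised is binomial(137, r), and the number normal is binomial among the unrevised. Each trial was tested both ways.

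| Assumed r, CR/XP | Gap if counted as not normal | Significant only if left out | Significant only if counted | Disagree |
|---|---|---|---|---|
| 1%/1% | 16.8 points | 1.8% | 0.8% | 2.6% |
| 2%/2% | 16.7 | 3.0% | 1.0% | 4.0% |
| 1%/2% | 16.0 | 4.9% | 0.3% | 5.2% |
| 1%/3% | 15.2 | 8.9% | 0.1% | 9.0% |
| 2%/5% | 14.2 | 15.0% | 0.1% | 15.1% |
| 5%/2% | 18.6 | 0.5% | 4.6% | 5.1% |

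At equal rates the gap shrinks by 17.0·r, so by 0.17 points at 1% and 0.34 at 2%.

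**3. Single data sets** (constructed; Pearson chi-square without continuity correction; XP v CR, 137 knees per arm).
- 5 XP and 1 CR withdrawn: 102/132 v 90/136, p=0.044 if left out; 102/137 v 90/137, p=0.113 if counted as not normal.
- 1 XP and 5 CR withdrawn: 105/136 v 90/132, p=0.097 if left out; 105/137 v 90/137, p=0.045 if counted.
- A clear result, 4 XP and 2 CR withdrawn: 110/133 v 89/135, p=0.002; 110/137 v 89/137, p=0.004.

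So the choice can move a borderline result in either direction and leaves a clear one alone.

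**4. Power if such knees count as not normal.** Two versions: 137 per arm, and 137 + 153·r per arm, where the revised knees were part of the 10% allowance and return to the denominator. At 2%/2%: 87.8% and 88.5%. At 1%/3%: 81.0% and 81.9%. If 0.66 and 0.83 already count revised knees as not normal, planned power stays at 90.2%.

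**The case against.** The best defence is that 8.1 already points to an answer: sizing for 137 followed knees implies that knees not followed are left out. That is fair, and it is why the handling is best called implied and not simply absent. But a sample size allowance is not an analysis rule, and it groups removals with patients who merely fail to return.

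The second defence is size. Early metal revision may be rare, the larger figures above need differences of 2 to 3 points between arms, and the borderline examples are constructed, with left-out gaps of 11.1 and 9.0 points instead of the planned 17. This stands, and it limits the weight of the point. It does not remove it, because the documents give no rate to rely on and the remedy costs almost nothing.

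Third, counting a revised knee as not normal is one defensible choice among others. That also stands: what needs correcting is the silence, and the specific rule is a recommendation.

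A reader might go further and infer that the plan expressly excludes revised knees, that it favours XP, or that it hides device failures. The documents support none of these. No sentence excludes such knees, there is no information on which arm would have more early failures, and revisions are reported through survivorship, complication rate, adverse event forms and the annual report.

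**Conclusion.** The point holds as a cheap improvement. Knees with the most serious device failures are withdrawn, and the implied but unstated handling removes them from the primary test with no sensitivity analysis. If these withdrawals differ by arm, the arm with more of them looks better than it would if they counted as not normal. This does not mean that it looks better than the other arm.

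The effect is small at equal low rates and becomes material only when the arms differ by a few points. All of this rests on assumed revision rates and on 66% and 83% holding among unrevised knees. It concerns only knees revised before the primary assessment, a time point that sections 1.4, 2.5 and 8.2 leave unnamed.

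**What to change.** In 8.2, state that in the comparison of knees as randomized:
- a knee with removal or metal revision before the primary assessment counts as not normal;
- a sensitivity analysis leaves such knees out;
- the number of such knees per arm is reported beside the primary result.

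If the sponsor prefers to compare unrevised knees only, 8.2 should say so and still report the numbers per arm.

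Two things are needed for the rule to work. The sponsor must name one primary time point. The analysis set must also be usable: sections 3 B and 3.3 treat randomization failures after the first bony cut as enrolled and followed, while 15 I lists them as withdrawals, and these passages must be reconciled. Deaths, rescinded consent and missed visits need their own rules, which this point does not settle.

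In 8.1, say whether 0.66 and 0.83 already count revised knees as not normal, and restate the power if they do not.

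The cost is a few sentences. No new data are needed, because for a metal revision the withdrawal form already records "date of revision, all component part numbers removed, and reason for revision", and it records the same items for a removal. The price is slightly lower rates of normal knees and, if the planning proportions do not already allow for revisions, the power loss shown above: from 90.2% to about 88% at an assumed 2%/2%, or to about 81% to 82% at 1%/3%.

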### **5. PROTOCOL DEVIATION MANAGEMENT AND REPORTING**

Protocol deviations will be documented on a protocol deviation form. Sites and the sponsor may document protocol deviations. Any protocol deviation affecting patient treatment should be reported to the IRB as locally required. As this is not an investigational trial, protocol deviations affecting patient treatment are not anticipated, and out of window visits or missed visits will not be documented as protocol deviations.

### **6. ADVERSE EVENT MANAGEMENT AND REPORTING**

A record of all device related and serious adverse events, including details of the nature, onset, duration, severity, relationship to the device, relationship to the operative procedure and outcome, will be made on the relevant section(s) of the Adverse Event Form. The subject should be questioned about progress with previously reported adverse event(s) at each subsequent follow-up assessment visit. Definitions to be used for adverse event reporting are included in section 15. Any serious or unanticipated adverse events should be reported to the sponsor as soon as possible, as it is required to report unanticipated adverse events to the FDA within 10 days of knowledge of the event.

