### STUDY SUMMARY

TITLE	Randomized Controlled Clinical Outcomes of the Vanguard XP Bicruciate Knee System
DESIGN	Prospective Controlled Multi-Center
PURPOSE	Compare the clinical outcomes of the Vanguard XP Bicruciate Total Knee System to the Vanguard CR Total Knee System
OUTCOME MEASURES	Patient Perception of recovery, Operative Room Procedure Time, Intraoperative complications; Anterior Cruciate Ligament (ACL) status; knee stability; readmissions, adverse events, pain, patient satisfaction, quality of life
POPULATION	306 knees, 5 surgeons
ELIGIBILITY	Patients will be included according to FDA cleared labeling of device in accordance with indications and contraindications for use.
DURATION	The study is anticipated to last no longer than 12 years which will include time for enrollment, data collection through ten years of follow-up and data analysis.

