**D. Medical History and Demographic Data**

1. Demographic information will be collected. Medical history will be obtained and a physical examination will be performed (including height and weight). Current medications, diagnosis, previous surgery, contralateral knee status, and comorbidities will also be recorded. Patient contact information (mailing address, phone number, and email address) will be collected in order to administer PROMS surveys either when a patient is unable to return for a clinical exam, or after the 2-year visit when the PROMS questionnaire is the only data point required.

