**F. Clinical Outcomes**

1. Data to determine the clinical and functional performance of the device will be collected. Pre-operative and post-operative analysis will be compared using recognized and validated systems:
  - a. **Modified Knee Society Score**
    - i. The American Knee Society Score is part clinical exam and part patient administered assessment of the knee. The objective part of the score, also known as the "knee score," should be collected in the clinic by qualified personnel. The functional and pain scores can be collected in

the clinic or via phone or mailer. An additional assessment of the incidence of “anterior knee pain” has been added to this CRF as an exploratory endpoint but does not affect the score. The full score will be collected preoperatively and at each post-operative visit through 2-years. After the 2-year visit, the patient administered portion will be collected with the PROMS Questionnaire by phone, email, or mailer from the patient.

b. Patient Reported Outcome Measures “PROMS”

- i. A PROMS Questionnaire will be completed by the patient before surgery, and at each postop appointment indicated in the data collection table to assess the patient’s perception of their knee replacement. This survey can be collected in the office, over the phone, or via mailer. The preoperative questionnaire contains the SANE, EQ-5D, Oxford Knee Score, and KOOS (The FJS and Patient Satisfaction questionnaires are only completed post-operatively). The postoperative questionnaire contains the SANE, Patient Satisfaction, FJS, EQ-5D, Oxford Knee Score, and KOOS validated patient administered outcomes scores.

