**G. Safety**

1. Adverse Events: Please reference section **6**, and section **15** for Adverse event data collection method and definitions. Only serious and device related adverse events will be collected for this study. Patient hospital readmissions should be documented on an adverse event form, and the relation to the device documented.
2. Revisions / Removals: Please reference section **4** and section **15** for Revision / Removal data collection method and definitions.
3. Withdrawals: Please reference section **3.4** for detailed data collection methods, and section **15** for relative definitions.
4. Protocol Deviations: Please reference section **5** for Protocol Deviation data collection methods for this study.

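### The protocol text does not require sites to ask about new adverse events, and an absent adverse event form cannot be told apart from a question never asked

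*Combined protocol and SAP*

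**What the plan says.** The Study Summary names "readmissions, adverse events, pain, patient satisfaction, quality of life" among the outcome measures, and Section 1.3 lists readmissions as a focus of the study. The secondary endpoints in Section 2.5 include "Complication Rate, Pain Relief, Functional outcomes, Survivorship".

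On capture, Section 6 asks for "A record of all device related and serious adverse events, including details of the nature, onset, duration, severity, relationship to the device" and other details. It then gives its one rule on questioning: "The subject should be questioned about progress with previously reported adverse event(s) at each subsequent follow-up assessment visit". Section 2.7 G adds: "Patient hospital readmissions should be documented on an adverse event form, and the relation to the device documented". Table 2.6-A marks the adverse event form as needed at every column from operative to 10 years. It is never a scheduled entry.

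Section 2.4 says that the patient is blinded to treatment only until surgery has taken place.

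**The concern.** Section 6 says what to record once an event is known, but not how new events become known. The one question it prescribes concerns events already on file. A form completed only when needed leaves no trace when it is not completed, so its absence can mean either that nothing happened or that nobody asked. An analyst cannot separate the two afterwards.

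This matters because complications and readmissions are to be compared between arms. Events missed equally in both arms pull the two observed rates down and closer together, so a real excess is harder to see. Events missed unequally can create or hide a difference. Patients may learn their implant after surgery and the surgeon knows it. Without a common wording, what is asked and what is mentioned may depend on the arm.

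**Working it through.** **1. The plan's own figure.** The only sample-size figure is for the primary endpoint (Section 8.1: 0.66 vs 0.83, two-sided 0.05, 90% power). With mean proportion 0.745:

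n = [1.96·√(2·0.745·0.255) + 1.2816·√(0.66·0.34 + 0.83·0.17)]² / 0.17² = 136.1, rounded up to 137 per group. Allowing for 10% loss, 137/0.9 = 152.2, rounded up to 153.

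This agrees with the plan and is not touched by the present point.

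**2. The text on capture, side by side.**

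| Place | What it provides | Does it elicit or document new events? |
|---|---|---|
| Section 6 | Record all serious and device-related events; ask about progress of earlier ones | Duty to record, no method of asking |
| Section 2.7 G | Readmissions go on the adverse event form | Says where, not how they are found |
| Table 2.6-A | Form as needed | No entry for asked, none |
| Section 2.7 F | "The postoperative questionnaire contains the SANE, Patient Satisfaction, FJS, EQ-5D, Oxford Knee Score, and KOOS validated patient administered outcomes scores" | Lists outcome scores only |
| Section 2.7 H | Osteolysis or migration on film goes on an adverse event form | Yes, for these findings, on films through 2 years |
| Sections 3.4 and 4 | Withdrawal form for death, removal or metal-component revision | Second record for these events once known |
| Section 9 | Monthly completeness review of required milestones | An as-needed form has no expected entry to check |
| Section 5 | Missed visits are not logged as deviations | No |
| Section 13 | Data-quality monitoring at least annually | No search for unreported events is specified |

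Section 2.7 D describes the time "after the 2-year visit when the PROMS questionnaire is the only data point required". From then on, the clinic and film routes fall away as well.

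**3. Illustration on assumed rates.** The documents give neither event rates nor miss rates. Every rate below is an assumption, chosen only to show direction and rough scale.

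Power = Φ[(d − 1.96·SE₀)/SE₁], with SE₀ = √(2p̄(1−p̄)/n) and SE₁ = √([p₁(1−p₁)+p₂(1−p₂)]/n), n = 153 per arm.

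- True 8% vs 20%, full capture: SE₀ = 0.0397, SE₁ = 0.0391, so Φ(1.08) = 86%.
- The same with 30% missed in both arms, observed 5.6% vs 14%: SE₀ = 0.0340, SE₁ = 0.0337, so Φ(0.52) = 70%.
- With 20% missed, power is 76%; with 40% missed, 62%.
- True 5% vs 15%: 83% with full capture, 73% with 20% missed, 52% with 50% missed.
- True 5% vs 10%: 38%, 31% and 21% at the same capture levels.

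Unequal capture with equal true rates:

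- True 8%, with 20% missed in one arm and 40% in the other: 0.08 × 0.8 = 6.4% and 0.08 × 0.6 = 4.8%, a false ratio of 4.8/6.4 = 0.75. In patients, this is 153 × 0.064 = 9.8 against 153 × 0.048 = 7.3, a gap of about 2.4.
- True 10%: capture of 90% vs 70% gives a false difference of 2 points; 80% vs 50% gives 3 points.

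**The case against.** The strongest reply is that the point argues from silence. The sentence on earlier events governs their follow-up, and does not limit what else a site may ask. Section 6 requires all serious and device-related events to be recorded, and a site that never asked would struggle to comply. This stands: a reader might infer that the protocol restricts questioning to old events, and it does not.

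A reader might also infer that new events come to light only if the patient volunteers them. The documents do not support that through 2 years. The objective Knee Society score is taken in clinic, films have their own trigger for an event form, Section 10.1 counts hospital and clinic records as source documents, and withdrawal forms record deaths, removals and metal-component revisions. The remaining gap in that period is mainly admissions elsewhere that go unmentioned.

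The case report forms are not part of the documents. Section 10.2 says that they exist and Section 13.1 that sites are trained on them, so a visit form might already carry a question on new events. The point therefore concerns the protocol text.

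Finally, the illustrative figures can be read as estimates of lost power or of bias. They are not. The 8% vs 20% contrast is favorable to showing a loss, since 5% vs 10% has only 38% power even with perfect capture. If 137 per arm remain after the planned 10% loss, the 86% and 70% become 82% and 65%. The 0.75 ratio needs one arm to miss twice as large a share as the other, and no passage shows that. No safety comparison is powered in the plan, and readmissions are not named in Section 2.5.

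What survives is that a duty to record does not make the asking uniform, and none of these routes leaves a record that the question was put.

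**Conclusion.** The point holds as a gap in the written collection method. The text does not require sites to ask about new events, and an absent form cannot be distinguished from a question not asked. Readmission and serious-event rates could be too low, and could be captured unequally between arms because patients are blinded only until surgery. Neither the amount nor the direction of any difference between arms can be derived from the documents. The conclusion rests on the protocol text alone and assumes that the unseen case report forms do not already close the gap. The primary endpoint and its sample size are unaffected. It is worth correcting because events lost at collection cannot be recovered in analysis, and the correction is cheap.

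**What to change.** Amend Section 6 so that at each visit or contact, including those by phone or mail, the patient is asked about any new hospital admission, operation or serious event since the last contact, as well as about progress of earlier events. The wording should be the same in both arms.

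In Table 2.6-A, add a required yes/no adverse event entry at each scheduled time point, with the full form completed when the answer is yes. The monthly completeness review in Section 9 then has an entry to check. If the case report forms already contain such an item, it is enough to state it in the protocol.

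Cost: a minor amendment, one scripted question and one field per time point. The downside is slightly more data entry and higher recorded event counts.
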